8.4 Preparation and Administration of Study Drug/Implantation of Study Device

The device in this study is the computer program that provides the CT-FFR interpretation of flow. The results will allow the physician to visualize flow through the coronary arteries and measure the level of obstructive disease. The physician will dictate a report based on his/her interpretation of the images. The report and a pdf of a major view of the coronaries will be maintained as part of the patient's medical record.

The use of the device requires no variance from the routine standard of care for CCTA. The CCTA results will be sent to HeartFlow for CT-FFR analysis if the physician finds that the patient has 30% to 100% obstructive disease based on CCTA standards.

8.5 Subject Compliance Monitoring

Study treatment regimen requires that the patient follow physicians' recommendations concerning follow-up care as described above. The study coordinator will monitor the patients to determine whether the patient follows the recommended treatment plan. If not, a study cardiologist will contact the patient and encourage compliance with the treatment plan.

8.6 Prior and Concomitant Therapy

Prior and concomitant medical therapy will be collected and documented at the time of patient referral to Lenox Hill Hospital Ambulatory Care CCTA Clinic as part of the medical history. The coordinator will also contact the patient 90 to 120 days after the CCTA exam and interview the patient on follow up care, including any additional medical interventions. Specifically, the coordinator will maintain a record of patients' documented cardiac risk history and track cardiac interventions for obstructive disease, including PCI and CABG during the study.

8.7 Packaging

n/a

8.8 Blinding of Study Drug/Device

This is not a blinded study, in terms of patient randomization into study cohorts. However, when patients are referred for CT-FFR, no information regarding the CCTA results will be provided to HeartFlow (the provider of CT-FFR services.) When Cardiologists interpret CCTA and Stress-MPI results, no information regarding CT-FFR results will be available to them for review.

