8.3 Method for Assigning Subjects to Treatment Groups

This is not a randomized study. Treatment assignments will follow the clinical protocol.

Once the CCTA results are interpreted by the physician, the physician will order CT-FFR exams for patients whose level of stenosis by CCTA standards is 30% to 100%.

If CT-FFR is positive patients will be referred for Cardiac Catheterization and invasive FFR.

If CT-FFR is negative, and level of obstruction is 30 to 49% by CCTA standards, patients will be referred to optimal medical care.

If CT-FFR is negative and level of obstruction is 50% to 70% by CCTA standards, patient will be referred for stress MPI. If stress MPI is positive patients will be referred for Cardiac Cath and invasive FFR. If stress MPI is negative, patients will be referred to optimal medical care.

If the patient has had a stress MPI within one year of the CCTA exam and the CCTA exam result is 50% to 70% obstructive, the physician will rely on the prior stress testing result, rather than repeating the stress test. If the stress testing results was negative, the patient will be referred to optimal medical care. If, in the investigator's opinion, the results indicate that the patient is at increased risk of obstructive disease, when considered with the CCTA findings, the patient will be referred to Cardiac Cath and Invasive FFR.

If CT-FFR is negative and level of obstruction is 70% to 100% by CCTA standard, patient will be referred to Cardiac Cath and Invasive FFR.

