8.9 Receiving, Storage, Dispensing and Return

8.9.1 Receipt of Drug Supplies/Device

The device will not be obtained. The CCTA imaging results will be sent to the HeartFlow computer for interpretation. Cardiologists participating in the study will have access to FFR images and results, and make their final recommendations based on these images.

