8.9.4 Return or Destruction of Study Drug/Device

:

At the completion of the study, there will be a final reconciliation of subjects who received FFR and those who did not, and related follow up testing and interventions. This reconciliation will be logged on a reconciliation form, signed and dated. Any discrepancies noted will be investigated, resolved, and documented.

9 Study Procedures

Figure 1 and Appendix 1 describe this information.

Patients scheduled for an outpatient CCTA to evaluate stable chest pain or angina and meet the study criteria will be asked to participate in the study. All study patients will receive a CCTA as part of standard of care.

A physician Cardiologist will interpret the CCTA as per current operating protocol. If the Cardiologist diagnoses stenosis in the range of 30% to 100%, the CCTA scan will be uploaded to Heart Flow for noninvasive FFR, via HIPAA compliant cloud-based technology reviewed and approved by the Northwell security team.

The Noninvasive CT-FFR is considered to be a research procedure at Northwell (though FDA approved) and is not part of the standard of care currently offered at Northwell. However, some institutions do use noninvasive CT-FFR as part of their standard of care. According to HeartFlow representatives, these include William Beaumont Hospital (Detroit), Sanger Heart and Vascular (Charlotte), Weill Cornell Medical College (New York), St Pauls Hospital (Vancouver) Cedars Saini (Los Angeles), Baylor Plano (Dallas), Sutter PAMF (SF Bay Area), Baylor St Lukes (Houston), Loyola Medical College (Chicago), Duke University (Durham), University Hospitals (Cleveland), and Minneapolis Heart Institute (Minneapolis).

Considering this, and the preliminary results of which we are aware, we believe that CT-FFR should be considered a minimal risk procedure.

Once the data has been analyzed by HeartFlow, the physician will receive a notification from HeartFlow that will allow for the physician to sign on to the HeartFlow server and analyze the flow of all vessels on an interactive program. The physician will interpret the HeartFlow results and the study coordinator will download the best quality phase on a PDF to be stored with the study report on RIS System. The physician will dictate an addendum to the CCTA scan discussing the CT-FFR findings.

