*Patients who have borderline obstructive disease (50% to 70% stenosis) who have negative CT-FFR will be referred for Stress MPI to confirm, unless the patient has had stress testing within a year of the CCTA. This is an accepted practice as part of the standard of care at Lenox Hill Hospital. If the stress test is negative, the patient will be referred to his/her physician for follow-up. If the stress test is positive, the patient will be referred to Invasive Coronary Angiography for Invasive FFR and diagnostic cardiac catheterization. If the patient has had a history of negative stress testing within a year of the CCTA, then the patient will be referred to his/her physician for follow-up. If the patient's prior stress test had findings that, in the investigator's opinion, increase the patient's risk of obstructive disease when viewed with the CCTA findings, the patient will be referred to Invasive Coronary Angiography for diagnostic cardiac catheterization and Invasive FFR. This is an accepted practice as part of the standard of care at Lenox Hill Hospital.**

Patients who have borderline obstructive disease (50% to 70% stenosis) who have positive FFR will be referred for Invasive Coronary Angiography for Invasive FFR and diagnostic

*cardiac catheterization. This is an accepted practice as part of the standard of care at Lenox Hill Hospital. **

Patients with 71% or greater stenosis will be referred for Invasive Coronary Angiography for Invasive FFR and diagnostic cardiac catheterization. This is an accepted practice as part of the standard of care at Lenox Hill Hospital.

**In current standard of care practice at Lenox Hill Hospital, for borderline obstructive coronary disease, the decisions as to whether to proceed with stress testing or refer to invasive coronary angiography is left to the medical discretion of the attending cardiologist.*

Invasive Coronary Angiography and Invasive FFR are considered to be the gold standard procedures for evaluation of obstructive coronary artery disease. Patients deemed to be at high risk for obstructive disease based on CCTA or Stress testing are referred for invasive testing to determine whether cardiac intervention consisting of Percutaneous Coronary Intervention or Coronary Artery Bypass Graft is necessary.

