In order to assess the primary endpoint of comparison of event rates for patients treated with CCTA and FFR-CT, we will perform a retrospective chart review of Invasive Coronary Angiograms performed at Lenox Hill Hospital from 2014 to 2018. We will specifically review Cardiac Catheterization reports to screen patients and record data for cases where the indication for Catheterization was (1) Positive stress test and/or (2) Positive CCTA. Based on the catheterization report we will determine whether the patient had obstructive coronary artery disease with/without flow limitation, in the same manner and following the same definitions as those used to categorize level of obstruction in subjects enrolled in the prospective cohort of the study.

This data will be used as comparison/control group to assess trends and rates of invasive coronary catheterization when no intervention is necessary, in cases where CCTA and/or stress test without CT-FFR was used to determine the need for cardiac catheterization. Only the minimum amount of data required for a robust comparison of event rates including the following identifiers -name, date of procedure and age will be collected.

9.1 Visit 1

1. Visit 1 is an ambulatory visit to Lenox Hill Outpatient CCTA Clinic. Consent for study participation will be collected and routine CCTA will be administered.

9.2 Visit 2

If CCTA shows < 30% obstruction, visit 2 will be a referral for optimal follow-up cardiac care. If CCTA shows 30 to 49% obstructive disease and CT-FFR is negative, visit 2 will be a referral for optimal follow-up care.

If CCTA shows 50% to 70% obstructive disease and CT-FFR is negative, visit 2 will be a referral for Stress MPI testing.

If stress testing has been performed in the past year, then the results of those test will be considered, and new stress testing will not be performed.

If prior stress test was negative, visit 2 will be a referral for optima follow-up cardiac care.

If the investigator assessed that the prior stress test results increase the risk of acute obstructive cardiac disease for the patient, Visit 2 will be a referral to cardiac catheterization and invasive FFR.

If CCTA shows $\geq 70\%$ obstructive disease visit 2 will be referral to cardiac catheterization and invasive FFR.

If CT-FFR is positive, visit 2 will be a referral to cardiac catheterization and invasive FFR.

9.3 etc.

Visit 3:

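### Section 8.8 promises stress-MPI reads without CT-FFR information, but the referral sequence in 8.3, 9 and 9.2 does not secure that blinding and no masking step is described

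*Combined protocol and SAP*

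**What the plan says.** Section 8.8 makes the blinding statement for both CCTA and stress MPI: "When Cardiologists interpret CCTA and Stress-MPI results, no information regarding CT-FFR results will be available to them for review".

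The referral rules are these:

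- Section 8.3, negative CT-FFR: "If CT-FFR is negative and level of obstruction is 50% to 70% by CCTA standards, patient will be referred for stress MPI".
- Section 8.3, positive CT-FFR: "If CT-FFR is positive patients will be referred for Cardiac Catheterization and invasive FFR".
- Section 8.3, after the MPI: "If stress MPI is positive patients will be referred for Cardiac Cath and invasive FFR". A negative MPI leads to medical care.
- Section 9 says that 50–70% patients "who have negative CT-FFR will be referred for Stress MPI to confirm", unless they had a stress test within the past year.
- Section 9.2 repeats the rule: "If CCTA shows 50% to 70% obstructive disease and CT-FFR is negative, visit 2 will be a referral for Stress MPI testing".

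On where the CT-FFR result goes, section 9 has a PDF stored with the report on the RIS, and adds: "The physician will dictate an addendum to the CCTA scan discussing the CT-FFR findings". Section 8.1 keeps the report and PDF in the medical record. Section 8.9.1 says: "Cardiologists participating in the study will have access to FFR images and results, and make their final recommendations based on these images".

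Two other sections bear on the point. Section 15.4 restates the blinding, but for CCTA reads only. Section 6.1 describes a different pathway, in which 30–100% lesions receive both stress MPI and CT-FFR and the MPI does not depend on the CT-FFR result.

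**The concern.** If MPI is ordered because CT-FFR was negative, the order can itself disclose the CT-FFR result to anyone who knows the patient is in the study. The result is also available in the systems the imaging team uses. The plan claims a masked read without saying how it is achieved.

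This read matters to the analysis. For a 50–70% patient with a negative CT-FFR who needs a new MPI, that MPI alone decides whether ICA follows. Section 14.2 calls the index test positive or negative according to whether the pathway leads to ICA, and section 6.2 counts as the primary event an ICA that turns out to need no intervention. A reader who leans towards a known negative CT-FFR would send fewer patients to ICA, which could favour the study hypothesis.

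The influence would act on one side of the comparison only. The historical controls in section 6.1 are catheterizations from 2014 to 2018 that followed a positive stress test and/or CCTA without CT-FFR, so their stress reads could not have been affected.

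**Working it through.** The main check is a comparison of sections.

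1. **What a new MPI reveals.** In 8.3 a positive CT-FFR leads to catheterization, and a negative CT-FFR with 50–70% stenosis leads to MPI. Within the 8.3, 9 and 9.2 rules, a new study MPI therefore implies a negative CT-FFR. One exception is that patients with no usable CT-FFR follow standard of care (7.6.1), and an MPI in them carries no such signal.
2. **Order of steps.** CT-FFR must be known before the MPI referral can be made. Section 9 describes the RIS storage and the addendum before the MPI step, but sets no timing rule for filing relative to the MPI read.
3. **Access.** Section 8.9.1 makes no exception for MPI readers. Section 5 describes one imaging team (six attendings, two cardiology fellows, one cardiac imaging fellow) with weekly research meetings.
4. **Barriers.** No section names a separate MPI reader, masks the requisition, or tells the reader not to open the CT-FFR report.
5. **The competing pathway.** Under 6.1, MPI does not depend on CT-FFR, so the promise in 8.8 could be kept there.
6. **The CCTA half of 8.8.** The first CCTA read comes before CT-FFR and decides whether CT-FFR is ordered, so it is not affected.

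For scale, the figures in section 14.1 reproduce:

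- ICA patients: n = [1.960·√(0.14·0.86) + 0.842·√(0.06·0.94)]² / (0.14 − 0.06)² = 120.99, so 121.
- CCTA patients: 121 / (0.60 × 0.35) = 576.2, against 576 stated.
- Negative ICAs among 121: 0.14 × 121 = 16.9 (about 17) and 0.06 × 121 = 7.3 (about 7).

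Suppose m MPI reads change from positive to negative, where m is assumed. The rate of negative ICAs per ICA then depends on which reads change:

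- If every changed read would have led to a negative ICA, the rate is (17 − m)/(121 − m): 13/117 = 11.1% at m = 4 and 7/111 = 6.3% at m = 10.
- If every changed read would have led to a positive ICA, the rate is 17/(121 − m): 17/117 = 14.5% at m = 4 and 17/111 = 15.3% at m = 10.

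The number of ICAs falls in both cases, but the rate per ICA can move either way. The first case is an extreme, in which ten reads would roughly equal the planned fall from 14% to 6%. The documents do not give the number of patients in the stratum, the share with a recent stress test, the MPI positivity rate or the likely shift, so m cannot be estimated.

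**The case against.** The strongest reply is that nothing shows the reader would actually be unmasked. The footnote in section 9 says that stress testing in borderline disease is already a discretionary option at this hospital. A reader who does not know the patient is enrolled would learn nothing from the requisition alone. Section 8.9.1 speaks of final recommendations rather than MPI interpretation, and no section says who reads MPI. Section 9 also defers to a figure and an appendix that could not be seen in this review. This stands against any claim that the reads are in fact unblinded, or that the CT-FFR result is always filed before the MPI is read. It does not supply the missing masking step.

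Section 6.1 is a second reply, and it stands in part. It offers a pathway on which 8.8 could be met, but it conflicts with 8.3, 9 and 9.2, which agree with one another on the MPI trigger.

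A third reply is that the index test is a composite of CCTA, MPI and CT-FFR, so masking one component from another is partly a design preference. That is fair, but the plan has stated the masking as a feature and should either deliver it or withdraw it.

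A reader might also infer three stronger points that the documents do not support:

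- **That reuse of a prior stress test also breaches 8.8.** That test was read before the CCTA and CT-FFR. The later judgement about referral need not be blind, but 8.8 covers interpretation of results and promises nothing about that judgement.
- **That a number of lost ICAs can be stated.** Only positive reads can shift to negative, and lost ICAs would include true positives, so they cannot be set directly against the 17 expected negative ICAs.
- **That unblinding is what leaves CT-FFR misses unverified.** MPI-negative patients get no ICA by design, even with a perfectly masked read.

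**Conclusion.** The point holds as a gap between a stated safeguard and the described workflow. Under 8.3, 9 and 9.2, the MPI blinding in 8.8 is not secured. Under 6.1 it could be, so the conflict between those sections has to be settled first.

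The possible bias is confined to new MPI reads in the 50–70%, CT-FFR-negative stratum, and to the prospective cohort. Its likely direction is towards fewer ICA referrals. Its size, and its net effect on the rate per ICA, cannot be derived from the documents. The conclusion rests on the text as written and assumes that no masking procedure appears in the missing figure or appendix. It should be corrected, because a report could otherwise claim a blinding that the procedures do not provide.

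**What to change.** First, reconcile section 6.1 with 8.3, 9 and 9.2 on when stress MPI is given. Which pathway is right is a clinical matter for the investigators.

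Then, if MPI still follows CT-FFR, add to 8.8 and 9:

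- The MPI requisition carries the CCTA findings and symptoms only, with no CT-FFR result and no study flag.
- The MPI is read and signed by a member of the existing team who did not interpret that patient's CT-FFR and does not open the CT-FFR report before signing.

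If this is not done, remove stress MPI from the blinding statement in 8.8 and report MPI as read with CT-FFR known, as a limitation.

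Filing of the CT-FFR addendum need not be delayed. Holding it back would keep a completed result out of the patient's record, and the reader instruction serves the same purpose. The cost is requisition wording and minor reader-assignment logistics, assuming that the team in section 5 reads the MPIs, which the plan should state. The alternative costs one edited sentence.

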8.9 Receiving, Storage, Dispensing and Return

8.9.1 Receipt of Drug Supplies/Device

The device will not be obtained. The CCTA imaging results will be sent to the HeartFlow computer for interpretation. Cardiologists participating in the study will have access to FFR images and results, and make their final recommendations based on these images.

8.9.2 Storage

n/a

8.9.3 Dispensing of Study Drug/Device

n/a

8.9.4 Return or Destruction of Study Drug/Device

:

At the completion of the study, there will be a final reconciliation of subjects who received FFR and those who did not, and related follow up testing and interventions. This reconciliation will be logged on a reconciliation form, signed and dated. Any discrepancies noted will be investigated, resolved, and documented.

9 Study Procedures

Figure 1 and Appendix 1 describe this information.

Patients scheduled for an outpatient CCTA to evaluate stable chest pain or angina and meet the study criteria will be asked to participate in the study. All study patients will receive a CCTA as part of standard of care.

A physician Cardiologist will interpret the CCTA as per current operating protocol. If the Cardiologist diagnoses stenosis in the range of 30% to 100%, the CCTA scan will be uploaded to Heart Flow for noninvasive FFR, via HIPAA compliant cloud-based technology reviewed and approved by the Northwell security team.

The Noninvasive CT-FFR is considered to be a research procedure at Northwell (though FDA approved) and is not part of the standard of care currently offered at Northwell. However, some institutions do use noninvasive CT-FFR as part of their standard of care. According to HeartFlow representatives, these include William Beaumont Hospital (Detroit), Sanger Heart and Vascular (Charlotte), Weill Cornell Medical College (New York), St Pauls Hospital (Vancouver) Cedars Saini (Los Angeles), Baylor Plano (Dallas), Sutter PAMF (SF Bay Area), Baylor St Lukes (Houston), Loyola Medical College (Chicago), Duke University (Durham), University Hospitals (Cleveland), and Minneapolis Heart Institute (Minneapolis).

Considering this, and the preliminary results of which we are aware, we believe that CT-FFR should be considered a minimal risk procedure.

Once the data has been analyzed by HeartFlow, the physician will receive a notification from HeartFlow that will allow for the physician to sign on to the HeartFlow server and analyze the flow of all vessels on an interactive program. The physician will interpret the HeartFlow results and the study coordinator will download the best quality phase on a PDF to be stored with the study report on RIS System. The physician will dictate an addendum to the CCTA scan discussing the CT-FFR findings.

*Patients who have borderline obstructive disease (50% to 70% stenosis) who have negative CT-FFR will be referred for Stress MPI to confirm, unless the patient has had stress testing within a year of the CCTA. This is an accepted practice as part of the standard of care at Lenox Hill Hospital. If the stress test is negative, the patient will be referred to his/her physician for follow-up. If the stress test is positive, the patient will be referred to Invasive Coronary Angiography for Invasive FFR and diagnostic cardiac catheterization. If the patient has had a history of negative stress testing within a year of the CCTA, then the patient will be referred to his/her physician for follow-up. If the patient's prior stress test had findings that, in the investigator's opinion, increase the patient's risk of obstructive disease when viewed with the CCTA findings, the patient will be referred to Invasive Coronary Angiography for diagnostic cardiac catheterization and Invasive FFR. This is an accepted practice as part of the standard of care at Lenox Hill Hospital.**

Patients who have borderline obstructive disease (50% to 70% stenosis) who have positive FFR will be referred for Invasive Coronary Angiography for Invasive FFR and diagnostic

*cardiac catheterization. This is an accepted practice as part of the standard of care at Lenox Hill Hospital. **

Patients with 71% or greater stenosis will be referred for Invasive Coronary Angiography for Invasive FFR and diagnostic cardiac catheterization. This is an accepted practice as part of the standard of care at Lenox Hill Hospital.

**In current standard of care practice at Lenox Hill Hospital, for borderline obstructive coronary disease, the decisions as to whether to proceed with stress testing or refer to invasive coronary angiography is left to the medical discretion of the attending cardiologist.*

Invasive Coronary Angiography and Invasive FFR are considered to be the gold standard procedures for evaluation of obstructive coronary artery disease. Patients deemed to be at high risk for obstructive disease based on CCTA or Stress testing are referred for invasive testing to determine whether cardiac intervention consisting of Percutaneous Coronary Intervention or Coronary Artery Bypass Graft is necessary.

In order to assess the primary endpoint of comparison of event rates for patients treated with CCTA and FFR-CT, we will perform a retrospective chart review of Invasive Coronary Angiograms performed at Lenox Hill Hospital from 2014 to 2018. We will specifically review Cardiac Catheterization reports to screen patients and record data for cases where the indication for Catheterization was (1) Positive stress test and/or (2) Positive CCTA. Based on the catheterization report we will determine whether the patient had obstructive coronary artery disease with/without flow limitation, in the same manner and following the same definitions as those used to categorize level of obstruction in subjects enrolled in the prospective cohort of the study.

This data will be used as comparison/control group to assess trends and rates of invasive coronary catheterization when no intervention is necessary, in cases where CCTA and/or stress test without CT-FFR was used to determine the need for cardiac catheterization. Only the minimum amount of data required for a robust comparison of event rates including the following identifiers -name, date of procedure and age will be collected.

9.1 Visit 1

1. Visit 1 is an ambulatory visit to Lenox Hill Outpatient CCTA Clinic. Consent for study participation will be collected and routine CCTA will be administered.

9.2 Visit 2

If CCTA shows < 30% obstruction, visit 2 will be a referral for optimal follow-up cardiac care. If CCTA shows 30 to 49% obstructive disease and CT-FFR is negative, visit 2 will be a referral for optimal follow-up care.

If CCTA shows 50% to 70% obstructive disease and CT-FFR is negative, visit 2 will be a referral for Stress MPI testing.

If stress testing has been performed in the past year, then the results of those test will be considered, and new stress testing will not be performed.

If prior stress test was negative, visit 2 will be a referral for optima follow-up cardiac care.

If the investigator assessed that the prior stress test results increase the risk of acute obstructive cardiac disease for the patient, Visit 2 will be a referral to cardiac catheterization and invasive FFR.

If CCTA shows $\geq 70\%$ obstructive disease visit 2 will be referral to cardiac catheterization and invasive FFR.

If CT-FFR is positive, visit 2 will be a referral to cardiac catheterization and invasive FFR.

9.3 etc.

Visit 3:

If patient receives a stress MPI, and it is negative, visit 3 will be referral to optimal follow-up care.

If patient receives a stress MPI, and it is positive, visit 3 will be to cardiac cath and invasive FFR.

If patient undergoes a cardiac cath and invasive FFR at visit 2, visit 3 will be a referral to optimal follow-up care.

Visit 4: If patient receives a cardiac cath with invasive FFR at visit 3, visit 4 will be to optimal follow-up care.

10 Risks to Subjects

The risks to subjects in this study are minimal, compared to the risks faced by the population of patients receiving standard of care for potential coronary artery disease and stable chest pain or angina at Lenox Hill Hospital. Most patients will receive the standard of care currently in place, but will have an additional test run (CT-FFR). This test does not require any additional activity of the patient beyond completion of the CCTA with contrast (Standard of Care). This test will be used to assess whether improvements in the standard of care can be made for future patients.

A small percentage of patients, those who have positive CT-FFR, but 30 to 49% obstructive disease by CCTA standard will undergo an additional invasive exam. This exam may identify obstructive disease. If so, the patient will benefit. If not, the patient will undergo an invasive procedure unnecessarily. We believe that very few patients, if any, will fall into this category.

Patients who undergo Invasive FFR and Diagnostic Cardiac Catheterization will face increased risk, as compared to standard of care. According to the NIH National Heart Lung and Blood Institute, this procedure is very common, and rarely causes serious problems. [22] However, complications can include bleeding, infection and pain at the catheter insertion site. On rare occasions the catheter can scrape or poke a hole in a blood vessel during insertion

causing damage to the blood vessel. Patients may also experience an allergic reaction to the dye that is used during the procedure. Less common reactions include arrhythmias, or irregular heart beats; kidney damage caused by the dye that is used during the procedure; blood clots that can trigger stroke or heart attack or other serious problems; low blood pressure; or a buildup of fluid in the sac that surrounds the heart. This may cause the heart not to beat properly. [22]

The anticipated benefit of this study is to identify a more accurate means of diagnosing coronary artery disease without invasive procedures and with less exposure to radiation. The use of CT-FFR should address the weakness of CCTA – its lack of specificity. CT-FFR is expected to increase the test's positive predictive value. We believe that the use of this technology can make significant reductions in the use of diagnostic cardiac catheterization without intervention and in the use of stress MPI to validate uncertain findings when CCTA is used as a first test.

11 Potential Benefit to Subjects

A small percentage of patients, those who have positive CT-FFR, but 30 to 49% obstructive disease by CCTA standards will undergo an additional invasive exam. This exam may identify obstructive disease. If so, the patient will benefit from treatment of obstructive disease. If not, the patient will undergo an invasive procedure unnecessarily. We believe that very few patients, if any, will fall into this category.

The anticipated benefit of this study is to identify a more accurate means of diagnosing coronary artery disease without invasive procedures and with less exposure to radiation in the future. The use of CT-FFR should address the weakness of CCTA – its lack of specificity. CT-FFR is expected to increase the test's positive predictive value. We believe that the use of this technology can make significant reductions in the use of diagnostic cardiac cath without intervention and in the use of stress MPI to validate uncertain findings when CCTA is used as a first test.

12 Research Related Harm/Injury

The only possible research related injury we can identify would be an adverse reaction to a cardiac cath procedure that a patient might not have otherwise undergone, if not participating in the study. We expect few if any of these procedures. Standard treatments for adverse reaction to cardiac cath would apply if such an event occurs. Patients will be informed of this risk at the time of obtaining informed consent. The consent states that the patient would be financially liable if such an event were to occur.

13 Provisions to Protect Privacy Interests of Subjects

We have described above the method of recruitment. Because the recruitment will be added to the process of care for patients already scheduled for a diagnostic workup, we do not believe there is a risk for invasion of privacy. When contacting patients by telephone, we will not disclose the purpose of our call, except to the patient, and leave the message specifically for the subject who we need to contact. All email or certified mail communications will be addressed explicitly to the subject. We will obtain permission to contact the subject as part of the informed consent process.

14 Statistical Plan

